3.5.2 Secondary endpoints

Safety: The following endpoints will be evaluated by group and overall:

- incidence, type, causality and severity of solicited adverse events for days 0-7 in Groups 1 and 2 combined and days 28-35 in Group 2;
- incidence, type, causality and severity of solicited adverse events for days 0-7 in Groups 3 and 4 combined and days 28-35 in Group 4;
- incidence, type, causality and severity of solicited adverse events for days 0-7 and days 28-35 in Groups 5, 6 and 7;
- incidence, type, causality and severity of unsolicited adverse events throughout the study period in all groups;
- incidence, causality and description of deviations from normal safety labs at Day 0, Day 7, Day 14 and Day 28 for Groups 1 through 4, and at Day 35, Day 42 and Day 56 for Groups 2 and 4;
- incidence, causality and description of deviations from normal safety labs at Day 0, Day 7, Day 14, Day 28, Day 35, Day 42 and Day 56 for Groups 5, 6, and 7.

Immunogenicity:

- Median titers of type 2 polio antibodies at Day 28 in Groups 1 and 2 combined;
- Median titers of type 2 polio antibodies at Day 28 in Groups 3 and 4 combined;
- Median titers of type 2 polio antibodies at Day 28 in Groups 5, 6 and 7.
- Seroprotection rate and median titers of type 2 polio antibodies at Day 56 in Groups 2 and 4;
- Seroprotection rate of type 2 polio antibodies at Day 28 and at Day 56 in Groups 5, 6 and 7.
- Seroconversion rate of type 2 polio antibodies at Day 28 for Groups 1 and 2 combined and at Day 56 in Group 2;
- Seroconversion rate of type 2 polio antibodies at Day 28 for Groups 3 and 4 combined and at Day 56 in Group 4;

- Seroconversion rate of type 2 polio antibodies at Day 28 and at Day 56 for Groups 5, 6 and 7. Seroconversion is defined as a change from seronegative to seropositive and neutralizing antibody titers of $\geq 1:8$, and in seropositive subjects, as an antibody titer increase of ≥ 4 -fold over baseline titers.

3.5.3 Exploratory endpoints

- GMT of type 2 polio antibodies at Day 28 in Groups 1 and 2 combined and at Day 56 in Group 2;
- GMT of type 2 polio antibodies at Day 28 in Groups 3 and 4 combined and at Day 56 in Group 4;
- GMT of type 2 polio antibodies at Day 28 and at Day 56 in Groups 5, 6 and 7.
- Viral shedding positivity rate (as determined using quantitative PCR) will be assessed at a pre-specified subset of the stool collection time points
- Median 50% cell culture infective dose (CCID₅₀; titer) of shed virus after viral extraction from PCR-positive stool samples will be assessed at a pre-specified subset of the stool collection time points
- Time-to-cessation of viral shedding will be assessed following each dose
- The extent of shedding, including quantity and duration, will be assessed among pre-specified stool collection time points following each dose.

Exploratory endpoints will include assessment for neurovirulence of shed virus (as measured in animal model(s)) and will also include assessment of the genetic stability of the modified regions of shed virus in a subset of stool samples.

3.6 Randomization

All OPV-vaccinated subjects are to receive one of the nOPV2 candidates in a single blind manner and all IPV- vaccinated subjects are to receive one of the nOPV2 candidates or placebo in a double-blinded manner.

For the whole study duration all subjects and blinded study staff responsible for safety evaluation of IPV-subjects will not have any information of what has been administered. As the placebo can be distinguished from the vaccine candidates in packaging and color, reception of the vaccines, dose preparation and administration is done by a team of unblinded study personnel. Appropriate measures are taken at the site to ensure blinding of subjects and blinded team for the whole duration of the study.

Groups are enrolled sequentially such that subjects receiving candidate 2 are enrolled first (IPV and OPV groups simultaneously), followed by subjects receiving candidate 1. IPV-only vaccinated adults are randomized 2:1 to candidate 2 (Group 6) or placebo (Group 7), respectively, until 16 to 44 Group 6 subjects are enrolled, after which randomization 2:1 to candidate 1 or placebo commences for Groups 5 and 7. For OPV-vaccinated subjects, randomization to Groups 1 and 2 to receive candidate 1 ensues following complete randomized enrollment of subjects to Groups 3 and 4. In all cases, block randomization is used to ensure balanced randomization across time.

Allocation of each subject to a given group is described in a computer-generated randomization schedule prepared prior to start of the study by Assign Data Management and Biostatistics GmbH, [name] using nQuery Advisor®. Assign also provides the site with randomization and emergency envelopes.

3.7 Data Monitoring

An independent Data and Safety Monitoring Board (DSMB) is charged with monitoring the benefit-risk and data integrity of this trial, to inform the sponsor about recommendations for future clinical trial phases.

The DSMB has established stopping rules for safety prior to study start, which are continuously assessed. The DSMB will also monitor study enrollment, particularly for IPV-vaccinated subjects, and recommend truncation and/or closure of study groups if enrollment stagnates and when current enrollment is considered sufficient to meet study objectives and no safety signals occurred. The minimum number of IPV-vaccinated subjects agreed on by DSMB per candidate vaccine is 24. With a randomization of 2:1 for placebo the minimum study cohort size for Groups 5, 6 and 7 will be 16. In case of safety signals the DSMB reserves the right to reverse the truncated enrollment. The structure and content of the DSMB reports will agree between the sponsor and the DSMB, independent of this analysis.

4 Analysis Populations

4.1 Intention-to-Treat Population

The Intention-to Treat (ITT) population is defined as all subjects who are randomized according to randomized treatment assignment.

4.2 Total Vaccinated Population

The Total Vaccinated population (TVP) is defined as all subjects who are in the ITT population and who received at least one dose of study vaccine. Drop out from ITT to TVP will be described.

4.3 Per-Protocol Population

The Per-Protocol (PP) population consists of all eligible study participants who are in the TVP and who receive all of the immunizations scheduled for the group to which they are allocated and excludes those subjects who meet any of the criteria outlined in protocol Section 5.3. All deviations and violations occurring in the study will be reviewed prior to database lock and classified as either minor or major. The PP population requires adherence to all vaccinations (including timing) for those from Groups 1, 3, 5 and 6, but subjects will not be removed from the population for missing outcome assessments; these will be handled case by case as missing data. In case of missing second vaccination of a subject in a 2-dose Group (Groups 2 and 4) but adherence to the protocol until that timepoint, all previous collected data will still be analyzed in the PP population. A subject matching items under protocol Section 5.3 will be removed from the PP analysis.

The TVP will be used for primary safety analysis and the PP population for primary immunogenicity analysis; all immunogenicity analyses (primary and secondary) will be repeated in the TVP.

5 Statistical Considerations

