5.3 CRITERIA FOR ELIMINATION FROM THE PER-PROTOCOL POPULATION

Subjects meeting the following criteria will be excluded from the Per-protocol analysis population (see Section 10.1):

- Any disease or therapy that, in the investigator's opinion, could significantly affect the subject's immune status.
- positive hepatitis panel (including hepatitis B surface antigen [HBsAg] and anti-hepatitis C virus [HCV] antibodies), positive HIV antibody screens or total serum IgA below lab lower limit of normal (LNN).
- administration of any vaccine other than the study vaccine within 28 days of the first dose of study vaccine and during the entire study period. Immunogenicity data from subjects receiving a non-study vaccine will be included in per-protocol population analyses up to the time of receipt of the non-study vaccine.

These subjects will be included in the Total Vaccinated population (see section 10.1) and will continue in the study for safety follow-up and will not receive further vaccine doses.

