6.7 Viral Shedding Analyses

Viral shedding analyses will be descriptive in nature and will include hypothesis tests contrasting nOPV2 recipients with mOPV2 recipients as defined below. The total vaccinated population will be used for viral shedding analyses following the first dose, and the per-protocol population will be used for viral shedding analyses following the 2nd dose. As above, post-dose-1 (pre-dose-2) samples will be combined within vaccine candidate and prior vaccination history, where relevant (combined Groups 1 & 2 for each of UAM1 and UAM4, combined Groups 3 & 4 for UAM4).

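### As written, the per-protocol rule discards valid Day 28 results in Groups 5 to 7 after a missed second dose, and its Section 5.3 removal sentence conflicts with that section's own carve-out for non-study vaccines

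*SAP*

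**What the plan says.** The PP population is the primary population for immunogenicity. SAP 4.3 builds it in layers, and Protocol 10.1 carries the same rule.

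- Base sentence, all groups: PP subjects are those "who receive all of the immunizations scheduled for the group to which they are allocated and excludes those subjects who meet any of the criteria" in Protocol 5.3.
- Timing clause: "The PP population requires adherence to all vaccinations (including timing) for those from Groups 1, 3, 5 and 6".
- Exception: "In case of missing second vaccination of a subject in a 2-dose Group (Groups 2 and 4) but adherence to the protocol until that timepoint", in which case "all previous collected data will still be analyzed in the PP population".
- Removal sentence: "A subject matching items under protocol Section 5.3 will be removed from the PP analysis".

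Protocol 5.3 opens by excluding subjects who meet its criteria. Its non-study-vaccine item then adds a limit of its own: "Immunogenicity data from subjects receiving a non-study vaccine will be included in per-protocol population analyses up to the time of receipt".

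The protocol's second Time and Events Schedule puts Groups 2, 4, 5, 6 and 7 on the same two-dose calendar. Its footnote places the Day 28 antibody sample before the Day 28 dose. SAP Section 7, which lists differences from the protocol, mentions only fold-rise summaries.

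**The concern.** A Day 28 titre drawn before dose 2 cannot be affected by whether or when dose 2 is given. Removing it because of dose 2 selects on an event after the outcome. That event need not be random: Protocol 5.4 bars further doses after, for example, a vaccine-related serious event.

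The plan avoids this selection in Groups 2 and 4 but not in Groups 5, 6 and 7, and gives no reason for the difference. Groups 5 and 6 appear beside the one-dose Groups 1 and 3, where a missed second dose cannot occur. The timing clause also names Groups 5 and 6 but not Group 7, although SAP 5.2 has PP membership reviewed blind for IPV-vaccinated subjects. That clause cannot be applied as written without knowing the allocation.

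The non-study-vaccine conflict matters for another reason. Groups 1 to 4 are followed to Day 42 or Day 70. A non-study vaccine given after the Day 28 sample either leaves the primary result in PP or deletes it, depending on which sentence the analyst follows.

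**Working it through.** **Step 1. What the rule does, group by group**

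| Groups | Doses | Named in timing clause | Named in exception | Day 28 PP result after a missed dose 2 |
|---|---|---|---|---|
| 1, 3 | 1 | yes | no | not applicable |
| 2, 4 | 2 | no | yes | kept |
| 5, 6 | 2 | yes | no | removed |
| 7 | 2 | no | no | removed by the base sentence |

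The Group 7 entry assumes that a placebo dose counts as a scheduled immunization. The Groups 2 and 4 entry assumes that the exception overrides the base sentence, which is its evident purpose.

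**Step 2. Timing of dose 2**

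The timing clause omits Groups 2, 4 and 7 and gives no number of days for any group. The documents hold two conduct limits: a visit window of Day 28 ± 2 days, and postponement by at most 7 days (Protocol 5.4). The PP definition cites neither. If Day 56 is counted from Day 0 (assumed), dose 2 on Days 26 to 35 and serum on Days 54 to 58 put the sample 54 − 35 = 19 to 58 − 26 = 32 days after dose 2. Deviations are classed as minor or major, but the text does not say that major means exclusion. The gap bears on Day 56 titres and on shedding, because "the per-protocol population will be used for viral shedding analyses following the 2nd dose".

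**Step 3. Size in Groups 5 to 7**

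Planned size is 16 to 44 per group. Removing one subject from an observed rate moves it by at most 1/n: 1/16 = 6.25 points, 1/44 = 2.3 points. The maximum is special. From 15/16 = 93.8%, removing the only non-responder gives 15/15, a rise of 6.25 points; removing a responder gives 14/15 = 93.3%, a fall of 0.4. From 16/16 nothing changes.

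No rate of missed second doses is documented. Assuming 5%, 10% or 20%, the Day 28 PP count is:

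- planned 16: 15, 14 or 13
- planned 44: 42, 40 or 35

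If all are seroprotected, the lower 95% Clopper-Pearson limit is 0.025^(1/n): 79.4% at n = 16 against 76.8% at n = 14, and 92.0% at n = 44 against 91.2% at n = 40.

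**Step 4. The primary comparison**

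The plan's own figure (Protocol 10.2) is 77 evaluable per vaccine group: 95% in both arms, margin 10%, one-sided alpha 0.025, power 80%. By normal approximation, n = (1.960 + 0.842)² × (2 × 0.95 × 0.05) / 0.10² = 74.6, so 75, which is close to 77. The concern does not dispute that figure.

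With the exception in force, missed second doses cost Groups 1 to 4 no Day 28 data and the planned count stays at 100 per candidate. If the base sentence overrode the exception, the same assumed rates in the 50 two-dose subjects would leave about 98, 95 or 90. Power would be 89.5%, 88.5% or 86.8% instead of 90.1% (normal approximation), or about 81%, 81% or 79% instead of 83% (exact enumeration of the Miettinen-Nurminen test, equal arms).

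For the Section 5.3 conflict, take 95/100. Removing one responder gives 94/99 = 94.9%; removing one non-responder gives 95/99 = 96.0%. So the first such deletion moves the rate by at most about 1 point, against a 10-point margin. No frequency of non-study vaccination is given.

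**The case against.** The strongest reply is that little depends on this. The primary immunogenicity endpoint uses Groups 1 to 4 only. Immunogenicity in Groups 5 to 7 is secondary, and SAP 6.6.1 says it is described, not compared between groups. Every immunogenicity analysis is repeated in the Total Vaccinated population, and post-dose-1 shedding already uses it. All of that stands, and it limits the consequence. It does not make the rule correct for the population the plan calls primary.

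Three stronger readings are tempting, and the documents support none of them.

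- A reader might infer that the unequal treatment of two-dose groups biases the primary non-inferiority test. It does not: Groups 5 to 7 are not in that test, and Groups 2 and 4 keep their Day 28 data.
- A reader might infer that off-schedule second doses stay in the PP analyses of Groups 2 and 4. That is not shown. All deviations are reviewed before database lock, and SAP 5.2 applies principles from a UAM1 data review report that is not among the documents. What can be said is that no PP timing criterion is stated for these groups.
- A reader might infer that the SAP overrides the protocol on non-study vaccines. The tension already lies within the protocol, between Sections 5.3 and 10.1. It can also be read harmoniously, with the specific carve-out qualifying the general sentence. SAP 6.5 supports that intent, since it cuts safety data only after receipt of a non-study vaccine. But the text never says that the carve-out governs.

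**Conclusion.** The point holds with limited consequence. SAP 4.3 and Protocol 10.1, followed literally, remove a valid Day 28 PP result after a missed dose 2 in Groups 5, 6 and 7, and after an off-schedule dose 2 in Groups 5 and 6, while Groups 2 and 4 keep theirs. The affected outputs are secondary, descriptive Day 28 summaries, and the Total Vaccinated repeat retains the data. The number of subjects affected is unknown: the 5% to 20% range is an assumption, and the plan's 10% non-evaluability allowance belongs to the Groups 1 to 4 safety sample size.

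The part that can reach the primary endpoint is the Section 5.3 conflict, and only under the literal reading of the removal sentence. It would matter for a Group 1 to 4 subject given a non-study vaccine after the Day 28 sample. Both parts should be settled before the PP review, so that membership does not rest on a later choice between sentences.

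**What to change.** Amend SAP 4.3 and Protocol 10.1 together.

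1. Replace the group lists with one time-point-specific rule for Groups 2, 4, 5, 6 and 7: a subject is in PP at a visit if the doses due before that visit were given per protocol. This extends the missed-dose-2 exception to Groups 5, 6 and 7. Apply the same rule to UAM1 Group 2; Protocol 10.1 already lets this study's definitions supersede those of UAM1.
2. State the same dose-timing criterion for every two-dose group, including 2, 4 and 7. Reconcile it with the Day 28 visit window and the Protocol 5.4 postponement passage, and say how a major deviation maps to PP exclusion. Which limit applies is for the sponsor to settle.
3. Qualify the removal sentence rather than delete it: for non-study vaccines, only data after receipt leave PP. The sentence also covers the other Section 5.3 items, such as positive hepatitis or HIV screens and low IgA, and those exclusions stay unchanged.

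The cost is wording in two documents, with no new data or visits.

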5.1 General Principles

The study UAM1, conducted in a pre-OPV2 cessation period (2015-2016), was specifically designed to provide active control comparator data for both safety and immunogenicity for the OPV-vaccinated adults given the novel vaccine candidates in this study. For all endpoints for OPV-vaccinated subjects, summaries of data from this study will be presented alongside corresponding summaries from UAM1. Summaries of data from IPV-vaccinated subjects will be presented according to group (each candidate, and placebo), and have no historical control companion groups. Summaries of demographics, baseline characteristics, and immunogenicity data from this study will be prepared by site and overall, to assess comparability of sites. For OPV-vaccinated subjects, comparative analyses will be limited to comparison of each vaccine to the UAM1 Sabin 2 control; for IPV-vaccinated subjects, each candidate vaccine group will be compared to the placebo group for safety endpoints.

All data will be summarized and/or listed. Unless otherwise specified in this document, a two-sided type I error rate of alpha = 0.05 will be used for inferential methods, such as for the generation of confidence intervals.

Unless otherwise specified, descriptive statistics (n, mean, median, standard deviation, minimum, maximum) will be used to describe continuous variables, and frequencies and percentages will be used to describe categorical variables.

Statistical analyses will be generated using SAS®, version 9.4 or above.

Unless otherwise specified, tables will include presentation of results by time point and by group, and overall, when possible. Figures and tables which provide more than summary statistics may include neutral explanatory text to aid in their description of the underlying data.

Unless otherwise noted, “baseline” will refer to the day of first vaccination for all participants in all groups.

To the extent possible, unintended differences in terms collected on CRFs between the two studies will be aligned for summary and presentation, with any recoding of UAM1 terms clearly specified in the study report. Coded terms will use a common coding dictionary across the two studies.

5.2 Timing of Analysis

A final analysis of all data will be performed when all data are collected and the database is locked, following a blinded (for IPV-vaccinated subjects) review of criteria for membership in the per-protocol population. The same principles for deviation classification applied to subjects from study UAM1, documented in the data review meeting report and common between UAM1 and UAM4 protocols, will be used here.

Within background vaccination cohort (OPV vs IPV), enrollment in this study was sequential, with respect to candidate. A pre-scheduled unblinded DSMB safety review of data from OPV-vaccinated (n=100) and IPV-vaccinated subjects in Group 3, 4, 6, and 7 (receiving candidate 2) was held following accumulation of 14 days post-first-dose safety data on 24 IPV-vaccinated subjects (randomized 2:1, candidate 2:placebo), to enable age de-escalation in a subsequent study in children and infants. A similar unblinded DSMB safety review was held with updated data to include 14 day post-first-dose safety data from 26 additional subjects receiving candidate 1 or placebo (Groups 1, 2, 5, and 7), to enable age de-escalation in the subsequent phase II study with candidate 1.

5.3 Missing Data

In spite of best efforts to collect complete data for all study subjects, some data will be missing at the end of the trial. For this study, data will be assumed to be missing completely at random, and

no imputation of results will occur. If evidence suggests data are not missing completely at random, additional sensitivity analyses, such as multiple imputation, may be justified and performed as additional exploratory analyses to augment the primary results.

6 Planned Analyses

6.1 Subject Disposition

A CONSORT diagram will be used to describe the number of subjects: screened, enrolled by study group, receiving immunization, with complete ascertainment of serology endpoints, withdrawn or discontinued, and included in the three primary analysis cohorts (ITT, TVP, PP).

This diagram will be supplemented with a table summarizing these same data, by site and overall, including the reasons for withdrawal or discontinuation.

A listing and summary table of reasons for screen failures (inclusion/exclusion criteria violated) will be produced.

6.2 Demographic, Baseline Characteristics, and Concomitant Medications/Vaccinations

Descriptive statistics will be provided per group, overall and by-site, for demographic characteristics (age, height, weight, race, and gender) for each study population. All other initial subject characteristics (e.g., physical examination abnormalities, medical history, prior/ongoing medications) will be provided by group for participants in the Total Vaccinated Population.

Concomitant medications will be coded and summarized using the WHO Drug Dictionary, separately for all prior or ongoing medications as well as only those ongoing at study start, as well as listed.

Prior polio vaccination history will be tabulated. Any non-study vaccine given during the study period will be listed.

Medical history will be summarized and listed.

Baseline immunogenicity assessments, including seroprotection rates and type 2 \log_2 neutralizing antibody titers, will be summarized as described in Section 6.6.

Deviations from normal of baseline vital signs, physical exam, and clinical laboratory assessments will be summarized as described in Section 6.5.

6.3 Protocol Deviations

If protocol deviations occur, a listing of protocol deviations will be prepared, separately for non-subject-specific deviations and subject-specific deviations, including classification of status as either major or minor.

